3.2 Study Outcome Measures

3.2.1 Primary

The primary end point will be to achieve >=30% reduction (Yes/no) in monthly (28 days) average pain score from baseline to Visit 4 (the last monthly treatment cycle), compared to placebo. The daily pain intensity score will be measured on a 11-point (0-10) numeric rating scale (NPRS) and reported in the Daily Symptom Diary (DSD). The monthly mean pain intensity score will be determined from baseline (4 weeks/28 days), for each month during the 12 weeks of treatment.

The monthly mean pain intensity score will be calculated if a participant has at least 80% compliance with the DSD.

A relevant decrease in chronic pain showing a beneficial effect will be a reduction of >=30% from baseline in the average pain intensity score [29, 30].

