7.2.1 Randomization

The participant to be eligible requires to present symptoms of trigeminal neuropathic pain for a minimum of 3 months (12 weeks). In addition, the participant to be eligible is required to have 80% compliance with the Daily Symptom Diary for the baseline period after visit 0 and reported an average pain intensity score of 4/10 in where 0= no pain and 10= maximum pain imaginable on a numerical rating scale (0-10), during the 4 weeks/28 days baseline period prior randomization as specified in the inclusion criteria. Participants then will be randomly assigned to one of two groups (Erenumab or placebo) and will be scheduled for Visit 1. Visit 1 should be scheduled within a week after randomization.

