Extraoral chair side QST: The cotton swab test will test sensitivity to non-painful mechanical stimulation (low-sensitivity). With the use of a cotton swab, the skin will be gently stroked 3-4 times with strokes of 1-2 cm in length in the area of V1, V2 and V3 and we will compare responses between the non-painful side to the painful side to detect normosensitivity, hyposensitivity, hypersensitivity and allodynia.

The spatula test will test temperature sensitivity following the same procedure as in the other 2 tests and temperature will be applied for 2-3 seconds. It is performed with a spatula that will be cold not exceeding 5 degrees Celsius or heated in a water bath until is 40 degrees Celsius.

EEG Assessment

EEG assessment will be performed in all participants. In chronic pain patients, alpha rhythms are slower in frequency and elevated in power relative to matched, healthy controls[39, 40]. Within the alpha band, the frequency at which maximum power is displayed, known as peak alpha frequency (PAF), varies considerably amongst individuals [45]. We have shown that PAF predicts future pain sensitivity in multiple experimental pain models [41-43]. We will examine whether erenumab can modulate PAF and therefore mediate clinical effects. PAF is based on a 5-minute, eyes-closed resting state EEG.

Daily Symptom Diary

Participants will be asked to complete the Daily Symptom Diary at the end of each day starting at the baseline phase and through the entire study (visits 1-5). Participants should have at least 80% compliance with the DSD the entire month, the equivalent of 23 completed days.

The diary collects the participant's pain intensity (reported on a 0-10 numeric rating scale) and use of pain medication. Participants are required to complete a Daily Symptom Diary electronically or on paper and a new form will be used for each month of the study. These forms may be returned in person at study visits.

Outcome Measure Questionnaires

Listed in the Schedule of Events (Appendix A). Questionnaire forms on paper will be provided to the participants if an electronic form is not feasible.

Some questionnaires are self-administered, and others will be administered by trained study staff.

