Separate linear mixed models will be applied to test other secondary objectives (e.g., monthly mean pain scores, measures of daily activities and functions, etc.) and exploratory objectives (e.g., QST measures) where the outcome variables are continuous. The model and testing will be the same as described in the above primary objective. The use of mixed models will provide flexibility with regard to assumptions related to the covariance structure of the residuals and the presence of missing data for the repeated measures.

Descriptive statistics for safety measures will also be calculated. We will collect the following data for descriptive purposes and, if necessary, to use as covariates: Demographic information (age and race/ethnicity), rescue medication history, psychological factors and perceived change in overall status (PGIC).

Missing Data

Participants may miss specific data points for a variety of reasons such as a missed visit, early withdrawal from the study, or inability to evaluate an endpoint at a time point. If participants miss entering data in the DSD, the missing data will be imputed by the mean of observed daily data if the missing days are less than 80% within a month. If the missing days are more than 80%, the monthly measurement from the previous month will be carried forward to replace the missing value for continuous endpoints.

If there is significant dropout, we will identify baseline characteristics that differ between those dropped out and retained. Maximum likelihood methods will be used for primary analyses, which address non-informative dropout [missing at random (MAR)]. If "informative" dropout is present, we will consider sensitivity analyses that add these relevant baseline covariates to make the MAR assumption more plausible [50]

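### Section 12.3 scores a 28-day diary month on as few as 6 completed days, sections 3.2.1 and 8.1 set the threshold at 23, and nothing says which rule governs the Visit 4 month

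*Combined protocol and SAP*

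**What the plan says.** The primary endpoint (section 3.2.1) is a yes/no response: a fall of at least 30% in the 28-day mean pain score from baseline to Visit 4. Section 12.1 identifies the Visit 4 value as the month of diary data before that visit.

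Three statements decide when a month has a score:

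- Section 3.2.1: "The monthly mean pain intensity score will be calculated if a participant has at least 80% compliance with the DSD".
- Section 8.1: "Participants should have at least 80% compliance with the DSD the entire month, the equivalent of 23 completed days".
- Section 12.3, Missing Data: "the missing data will be imputed by the mean of observed daily data if the missing days are less than 80% within a month".

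When more than 80% of days are missing, section 12.3 adds that "the monthly measurement from the previous month will be carried forward to replace the missing value for continuous endpoints". The same section states that "Maximum likelihood methods will be used for primary analyses", on a missing-at-random assumption.

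The baseline month has its own gate in section 7.2.1: a participant is "required to have 80% compliance with the Daily Symptom Diary for the baseline period after visit 0".

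**The concern.** Sections 3.2.1 and 8.1 count completed days and section 12.3 counts missing days, yet both use 80%. The two thresholds therefore lie far apart. Between them is a wide band of months that one rule scores and the other does not provide for.

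The filling-in sentence in 12.3 is not limited to continuous endpoints; only the carry-forward sentence is. The conflict therefore reaches the Visit 4 responder status. Two programmers working from the same document could build different primary datasets, and the choice could be made after the data have been seen.

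**Working it through.** **Inputs.** Month length 28 days (3.2.1). Completion threshold 80% (3.2.1), stated as 23 days (8.1). Filling-in when fewer than 80% of days are missing, and carry-forward when more than 80% are missing (12.3). Planning rates 58% and 25%, with 20 participants per arm (12.2).

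**1. The plan's own figure.** 0.80 × 28 = 22.4, rounded up to 23 completed days. This reproduces section 8.1.

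**2. Section 12.3 as written.** Missing days must be below 22.4, so at most 22 are missing and at least 28 − 22 = 6 are observed (6/28 = 21.4% complete). Carry-forward needs at least 23 missing days, so 0 to 5 observed.

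**3. The disputed band.** Counts scored under 12.3 but below 23 run from 6 to 22, which is 22 − 6 + 1 = 17 of the 29 possible counts (0 to 28).

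**4. What filling-in does.** With k observed days of mean m, the filled month has mean [k·m + (28 − k)·m]/28 = m. The 6-day mean simply stands as the 28-day score. If days were independent with equal variance (an assumption), its standard error relative to a 23-day mean would be √(23/6) = 1.96 times as large.

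**5. Likely cause.** With a threshold of less than 20% missing, 0.20 × 28 = 5.6, so at most 5 days are missing and at least 23 observed. That is exactly the 8.1 rule, and the disputed band disappears.

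**6. Effect of one participant.** The two rules do not give opposite responses. One gives a response and the other gives none, so the participant enters or leaves the Visit 4 data. Near the planning rates, 58% of 20 is 11.6 (take 12) and 25% of 20 is 5:

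| Arm | All 20 | One responder left out | One non-responder left out |
|---|---|---|---|
| Erenumab | 12/20 = 60.0% | 11/19 = 57.9% (−2.1) | 12/19 = 63.2% (+3.2) |
| Placebo | 5/20 = 25.0% | 4/19 = 21.1% (−3.9) | 5/19 = 26.3% (+1.3) |

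The crude shifts run from 1.3 to 3.9 percentage points.

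**7. Visit windows.** Visits have a window of ±3 days. If months are counted from visit to visit, the bounds move a little. At 25 days, 0.80 × 25 = 20, so 20 completed days are needed and 12.3 accepts 6, giving a disputed band of 6 to 19. At 31 days, 0.80 × 31 = 24.8, so 25 are needed and 12.3 accepts 7, giving a band of 7 to 24. At 25 days with 5 observed, exactly 80% are missing and neither 12.3 sentence applies.

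**The case against.** **The rules may not collide.** Section 3.2.1 says *if*, not *only if*, and section 8.1 says participants *should* comply. Section 12.3 could then be the fallback when the target is missed. The wording allows this, so it would be too strong to say that 3.2.1 forbids scoring a shorter month. But on that reading the 80% condition in the endpoint definition does almost no work, and nothing states that 12.3 takes over. The need to settle the matter stands.

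**It is an obvious slip.** Probably, given step 5. But the next sentence of 12.3 repeats 80%, so the pair is coherent as written, and the document does not confirm the slip. A programmer should not have to guess.

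**Little will change in practice.** Only diary-compliant participants are randomised, and sections 7.3.2 to 7.4 check compliance at Visits 2 to 5, so short months may be few. The primary analysis is a repeated-measures mixed model, not a comparison of raw proportions. A month with 22 days is also nearly as informative as one with 23. All of this stands. It limits the likely effect on the result but does not tell the analyst which dataset to build.

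**Conclusion.** The plan is wrong as written: two unranked rules define the same outcome variable, and the months with 6 to 22 completed days include the one behind the primary endpoint. This should be settled before unblinding. The day counts are exact for a 28-day month. The shift of about 1 to 4 points is a crude illustration for one participant near the planning rates, not an estimate from the planned model. The factor of 1.96 rests on independent days. The document gives no basis for predicting how many disputed months there will be.

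Several stronger readings are tempting but unsupported:

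- **One reclassified participant moves an arm by 5 points (1/20).** The rules differ on whether a month is scored, not on which response it gets, so this is the wrong contrast.
- **Short months will misclassify responders at some stated rate, or bias the treatment effect.** This would need the day-to-day variability and autocorrelation of pain scores, which the document does not give. It would also compare a short month with a full month that neither rule produces.
- **Baseline scores are affected.** The randomisation requirement rules this out.
- **Carried-forward values decide the primary endpoint.** Section 12.3 limits carry-forward to continuous endpoints, and the primary endpoint is binary. For the continuous monthly mean, carry-forward does compete with the stated likelihood handling, which is a valid but secondary point.

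**What to change.** **Needed.** In section 12.3, state that the monthly mean is computed from the observed days only when at least 80% of that month's days are completed (23 of 28). Otherwise the month is missing and is handled by the maximum-likelihood methods already stated. This adopts the protocol's own threshold from 3.2.1 and 8.1. If months can differ from 28 days, say that the 80% applies to the actual number of days.

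**Secondary.** Drop the carry-forward sentence for the continuous monthly mean. Merely changing 80% to 20% in both 12.3 sentences would not be enough. More than 20% missing means at least 6 missing days, so carry-forward would widen from 0–5 to 0–22 completed days.

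**Optional.** Add a sensitivity analysis that counts missing Visit 4 responses as non-response. State whether the diary is collected at early termination: section 7.5 applies the Visit 4 procedures there, while Appendix A shows no diary-collection mark in that column. Neither step resolves the conflict.

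**Cost.** One corrected sentence and one deletion, with no new data collection. Months with 6 to 22 completed days become missing, and the loss of precision depends on how many there are. In a trial of 40 this could matter if they are common, so their number should be reported by arm and visit.

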5.5.2 Handling of Subject Withdrawals or Subject Discontinuation of Study Intervention

Participants withdrawn after randomization will not be replaced. Participants who are withdrawn voluntarily or by the investigator will be discontinued from the study.

Study staff will complete a study disposition form in the eCRF, indicating the reason for discontinuation.

If the patient is a patient from the school and/or is interested in following orofacial pain care at the Brotman Facial Pain clinic, will be referred to the faculty practice clinic front desk for information and to schedule an appointment if wants to.

Unblinding, if required, will be carried out according to the procedures described in Section 5.4.2. A participant who has an AE at the time of discontinuation will be followed until the event returns to baseline, resolves, or is stabilized. If the AE does not meet one of these outcomes within 30 days after discontinuation or the end of the study, the participant will be referred to an appropriate provider for continued medical care (See section 9.2).

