6.3 Modification of Study Product Administration for a Subject

If a dose of Erenumab is missed, will be administered as soon as possible. Thereafter, Erenumab will be scheduled monthly from the date of the last dose.

The safety profile of erenumab has been favorable in clinical trials and in the post-marketing setting. A limited number of adverse drug reactions (injection site reactions, constipation, muscle spasm, and pruritus) have been identified at low frequencies (< 5%) in clinical trials. In the long-term use of erenumab, the safety profile remained consistent through 5 years of open-label treatment. In post-marketing settings, hypersensitivity reactions (including rash, angioedema and anaphylactoid reactions) and constipation with serious complications have been reported. In addition, oral sores (eg, stomatitis, mouth

ulceration, oral mucosal blistering), alopecia and rash (eg, rash papular, exfoliative rash, rash erythematous, urticaria, blister) have been observed in post-marketing surveillance.

Adverse reactions with the use of Erenumab have been hypersensitivity reactions, constipation with serious complications and hypertension. Exclusion criteria includes medical history of constipation or taking medications associated with decrease of G.I motility as well as pre-existent hypertension (See 5.2). If the participant reports a hypersensitivity reaction (rash, angioedema, anaphylaxis), new onset constipation or new onset of hypertension or if the participant decides against using Erenumab, he/she will be discontinued from the study (See 2.3.1 and 5.5.2).

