6.6.4 Not allowed medications

Participants cannot take as rescue medication or start therapy with any oral antiepileptics, SSRIs, SSNRIs, MAOIs, tricyclics antidepressants, tizanidine, baclofen, prednisone during the study (Please see Appendix B). In addition, they cannot receive any nerve blocks, onabotulinum toxin A injections, or use prescription compound topicals (except the ones that can be used as rescue mentioned above) or drug infusions for the management of TNP.

Participants who are currently taking pain medication for TNP and the rescue medication was not helpful and are in need of other strategy due to TNP, they will need to be withdrawn from the study to follow up with TNP management (this being dosage adjustment of the medication they are currently taking for the management of TNP or other).

Participants who are not currently taking pain medication for TNP, and the rescue medication was not helpful and are in need of other strategy. They will need to be withdrawn from the study to follow up with TNP management.

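### The only planned response to informative dropout stays within missing at random, so it cannot show whether the primary result depends on that assumption

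*Combined protocol and SAP*

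**What the plan says.** The Missing Data paragraphs of Section 12.3 make maximum likelihood the primary approach and describe it as suited to non-informative (MAR) dropout. What follows is conditional. First, "If there is significant dropout, we will identify baseline characteristics that differ between those dropped out and retained". Then, if dropout is judged informative, "we will consider sensitivity analyses that add these relevant baseline covariates to make the MAR assumption more plausible". The plan defines neither how much dropout is significant nor how informative dropout would be recognised.

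The only other rules concern the diary. Missing days are filled with the mean of the observed days when less than 80% of the month is missing. Beyond that, "the monthly measurement from the previous month will be carried forward to replace the missing value for continuous endpoints".

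Elsewhere the protocol says who must leave. Section 6.6.4 covers participants whose rescue medication did not help and who need another strategy: "they will need to be withdrawn from the study to follow up with TNP management". Section 6.3 names a hypersensitivity reaction and then "new onset constipation or new onset of hypertension or if the participant decides against using Erenumab, he/she will be discontinued from the study". Section 5.5.2 adds: "Participants who are withdrawn voluntarily or by the investigator will be discontinued from the study". Section 7.5 provides an early termination visit with the Visit 4 procedures, subject to the participant's permission.

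**The concern.** Dropout is informative when, given everything observed, missingness still depends on the outcome that was not seen. Adding baseline covariates to a likelihood model changes what the model conditions on. It does not relax the assumption that leavers resemble comparable stayers. The step can therefore make MAR more credible, but it cannot show what happens to the result if MAR fails.

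That gap matters here because the required exits follow events after baseline: a reaction, or pain that rescue medication did not control. Baseline characteristics cannot record these events. The primary endpoint (Sections 3.2.1 and 12.1) rests on the diary month ending at Visit 4, and a participant who leaves before or early in that month will often have no such month. With 20 participants per arm, a handful of unobserved outcomes can move the primary difference materially, and the plan gives the reader no way to see by how much.

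**Working it through.** **Inputs.** From Section 12.2: 40 participants, 20 per arm; 15% overall dropout; response of 58% on erenumab and 25% on placebo. From Section 12.3: MAR likelihood analysis; a mixed model with Visits 2 to 4.

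**Step 1: the plan's own figures.** The plan states no figure for the effect of missing data. Its dropout rate gives 0.15 × 40 = 6 leavers and 34 stayers. Its response rates give a difference of 58 − 25 = 33 points and an odds ratio of (0.58/0.42)/(0.25/0.75) = 4.14, close to the stated 4.2. Whether 36 participants give the stated power is a separate matter and is not used here.

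**Step 2: how far the result can move.** Assume 58% and 25% among stayers and count every leaver as a non-responder. Rate per arm = (20 − leavers) × stayer rate / 20.

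| Leavers, erenumab/placebo | Erenumab | Placebo | Difference (points) |
|---|---|---|---|
| 3/3 | 17 × 0.58/20 = 49.3% | 17 × 0.25/20 = 21.25% | 28.05 |
| 4/2 | 16 × 0.58/20 = 46.4% | 18 × 0.25/20 = 22.5% | 23.9 |
| 2/4 | 18 × 0.58/20 = 52.2% | 16 × 0.25/20 = 20.0% | 32.2 |
| 6/0 | 14 × 0.58/20 = 40.6% | 25.0% | 15.6 |
| 0/6 | 58.0% | 14 × 0.25/20 = 17.5% | 40.5 |

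The stayers' difference is 33 points in every row. The rows are results under a composite rule. They are not the response rates that would have been seen had everyone stayed.

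**Step 3: can the planned step detect this?** A large simulation (all inputs assumed) used true Visit 4 response of 58% and 25%, a baseline covariate correlated 0.2 with the outcome, non-responders leaving with probability 0.15 in both arms, and a further 0.10 chance of leaving erenumab for a reaction. Overall dropout was about 14%.

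- Stayers: 62.0% vs 28.2%, difference 33.7 points.
- Adjusted for the baseline covariate: 61.9% vs 28.2%, difference 33.7 points.
- Leavers as non-responders: 52.2% vs 25.0%, difference 27.2 points.

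Adjustment moved the estimates by about 0.1 point or less and left both arms' rates too high by about 4 and 3 points. The simulation has no earlier visits, so it tests the covariate step alone and not the planned mixed model.

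**Step 4: can the covariates be found?** Comparing 6 leavers with 34 stayers on a baseline variable that differs by 0.8 SD, the standard error is √(1/6 + 1/34) = 0.443 SD and the noncentrality is 0.8/0.443 = 1.81. A two-sided 5% t test then has about 42% power. Relevant covariates would often be missed.

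**The case against.** **The mixed model already uses earlier months.** Lack of relief shows in diary scores, and dropout driven by recorded pain is MAR. This stands in part. In a simulation with assumed inputs (random-intercept logistic model, SD 2, 20,000 per arm, Visits 2 to 4, no reaction dropout), Visit 3 non-responders left with probability 0.25. The true difference was 34.2 points and the model gave 34.3. When Visit 4 non-responders left instead, with the same probability in both arms, the true difference was 33.3 and the model gave 33.9, although each arm's rate was about 5 points too high. A reader might infer that dropout here is informative by rule. The documents do not support that: they require exit after certain events but do not make those exits unpredictable from observed pain. Reaction withdrawals, and exits before any complete post-baseline month, are less protected.

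**The bias need not favour erenumab.** This stands. A reader might infer overstatement because reactions belong to the active drug. Sections 2.3.1 and 6.3 put the reactions identified in trials below 5% each, which is fewer than 0.05 × 20 = 1 participant per reaction. They give no rate for hypersensitivity or hypertension. If erenumab works, lack-of-relief exits should fall more on placebo. The figures therefore do not support a split heavily weighted to erenumab.

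**Data do not simply stop.** This stands as a qualification. Section 7.5 calls for the Visit 4 procedures at early termination, and Section 7.3.4 lists diary review among them. The early termination column of Appendix A marks no diary collection, so the two disagree. Either way, one visit cannot supply diary days that come after withdrawal.

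**Other rules may fill the gap.** Mean imputation with less than 80% missing allows 22 of 28 days (78.6%) to be missing, so 6 recorded days could yield a Visit 4 value. Carry-forward, if applied to the monthly score, could make a high-pain leaver a non-responder. The text limits it to continuous endpoints and does not say whether response is derived afterwards. Neither rule is offered as a test of MAR.

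**The cited reference on this point has pattern mixture models in its title.** The plan itself specifies no such model.

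**Conclusion.** The point holds in a limited form. The plan contains no analysis of the binary primary endpoint that departs from MAR in a stated way, and the one step offered for informative dropout cannot do that job. It is also optional, has an undefined trigger and relies on covariates chosen after dropout is seen.

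The size is illustrative: about 16 to 41 points across the possible splits of 6 leavers, 28 for an even split, against 33 among stayers. This rests on three assumptions: the Section 12.2 response rates apply to stayers, dropout equals the planned 15%, and every leaver counts as a non-responder. A reader might take the lower figures as the true effect. They are not: counting someone withdrawn for a reaction as a pain non-responder is a choice of estimand. The range shows how much the answer depends on who leaves and how they are handled, not that the likelihood analysis is biased by that amount or in a known direction. The MAR analysis remains reasonable as the primary one. This is a cheap improvement, not a fatal fault.

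**What to change.** Keep the MAR likelihood analysis as primary. Replace the last sentence of the Missing Data text in Section 12.3 with two pre-specified sensitivity analyses, run whatever the amount of dropout:

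- **Non-responder analysis.** Every randomised participant without an evaluable Visit 4 month because of withdrawal, for any reason, counts as a non-responder.
- **Delta-adjusted multiple imputation.** Impute the monthly pain score under MAR, shift the imputed values by an amount varied separately in each arm over a range the sponsor justifies, re-derive the 30% response, and report the tipping point at which the conclusion changes.

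Also state whether carry-forward applies to the monthly score from which the binary endpoint is derived. Define an evaluable month by reconciling the 80% compliance requirement in Section 3.2.1 with the 80% missing threshold in Section 12.3. Reconcile diary collection at early termination between Section 7.5 and Appendix A.

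The two analyses change no visit, dose or withdrawal rule. The cost is plan wording, a little programming, and the possibility of a less favourable sensitivity result.
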